This is a placebo-controlled, randomized controlled trial to investigate the role of vaginal cryotherapy on pelvic floor myofascial pain in women. This study involves randomizing patients who are found to have pelvic floor myofascial pain on examination into one of two treatment groups: transvaginal cryotherapy or transvaginal application of a room-temperature tube. Patients will be followed up at two different time points in order to assess response to treatment. Follow-up times include immediately after application (Specific Aim #1) and two weeks following use of the intervention alone (Specific Aim #2). Patients will be referred to pelvic floor PT, which is considered the standard of care for treatment of pelvic floor myofascial pain at this time. As it typically takes 2-3 weeks to get in to see one of the pelvic floor PT providers at Wash U, follow up for this study will be completed prior to their attendance at pelvic floor PT.

E2 Subject Selection and Withdrawal

2.a Inclusion Criteria

Study population and eligibility: All new patients presenting to our facility undergo our standardized pelvic floor myofascial examination and are asked to rate their pain on palpation of the bilateral OI and LA muscles on a 0-10 verbal pain rating scale (0=none 1-3=mild, 4-6=moderate, and 7-10=severe). Patients found to have pelvic floor myofascial pain of at least 4/10 in severity at any of the four sites will be eligible for inclusion. Eligible patients may participate in Specific Aim 1 only or in both Specific Aims 1 and 2.

2.a Exclusion Criteria

Exclusion criteria include age <18, non-English speaking, current diagnosis of dementia, and limited physical mobility that would prevent full participation in pelvic floor PT. Patients will also be excluded if they have performed vaginal cryotherapy in the past or present with a complaint or known history of chronic pelvic pain.

2.b Ethical Considerations

Human Subjects Involvement and Characteristics

We will approach adult women presenting to the FPMRS Clinic at Washington University in St. Louis for inclusion. Eligible women will be ≥ 18 years old, English speaking, found to have pelvic floor myofascial pain on examination, and willing to participate.

Inclusion of Women, Minorities, and Children

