All new patients presenting to our facility undergo our standardized pelvic floor myofascial examination and are asked to rate their pain on palpation of the bilateral OI and LA muscles on a 0-10 verbal pain rating scale (0=none 1-3=mild, 4-6=moderate, and 7-10=severe). Patients found to have pelvic floor myofascial pain of at least 4/10 in severity at any of the four sites will be considered eligible and approached for study inclusion. Exclusion criteria include age <18, non-English speaking, current diagnosis of dementia, limited physical mobility that would prevent full participation in pelvic floor PT, complaint or known diagnosis of chronic pelvic pain or prior use of vaginal cryotherapy. We will enroll a total of 66 patients for the trial.

F2 Schedule of Measurements

Data collection will occur at baseline and 2 weeks (**Figure 2**). Patients will complete validated questionnaires including the short forms of the Pelvic Floor Distress Inventory (PFDI-20), Pelvic Floor Impact Questionnaire (PFIQ-7), and Pelvic Organ Prolapse/Urinary Incontinence Sexual Questionnaire IUGA-Revised (PISQ-IR, 24, 25). Questionnaires will be scored according to published protocols (26, 27). (see attached)

F3 Safety and Adverse Events

The risks of the proposed study primarily include discomfort and embarrassment with the pelvic examination. This risk is not unique to study participants as all new patients undergo a comprehensive pelvic floor myofascial examination. Participants may also experience discomfort or embarrassment with intravaginal tube placement. Finally, breach of confidentiality is another risk. Every precaution will be taken to ensure data are kept strictly confidential. Only the research team will have access to paper data, which will be stored in a locked cabinet in the FPMRS offices. Enrolled patients will be assigned unique study identification numbers. A password-protected electronic database will be established using REDCap, and only the research team will have access. No results will be presented in a personally identifiable manner.

3.a Safety and Compliance Monitoring

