Grade IV	Life-threatening complication (including CNS complications)* requiring IC/ICU management
Grade IVa	Single organ dysfunction (including dialysis)
Grade IVb	Multiorgan dysfunction
Grade V	Death of a patient
Suffix "d"	If the patient suffers from a complication at the time of discharge (see examples in Table 2), the suffix "d" (for "disability") is added to the respective grade of complication. This label indicates the need for a follow-up to fully evaluate the complication.

*Brain hemorrhage, ischemic stroke, subarachnoidal bleeding, but excluding transient ischemic attacks.
CNS, central nervous system; IC, intermediate care; ICU, intensive care unit.

F4 Study Outcome Measurements and Ascertainment

The data collected will include demographic characteristics; basic medical and reproductive health histories; pre- and post-treatment myofascial examination scores; PFDI-20, PFIQ-7, and PISQ-IR results at baseline and follow up visits; PGI-I and SAPS scores at study conclusion; PFPT assessments. Demographic data, medical and reproductive health histories, and pre- and post-treatment myofascial examination scores will be obtained from the medical record. Baseline questionnaires will be completed by the patient electronically directly in REDCap using a secure, password-protected tablet owned and operated by the research team. Follow up surveys and questionnaires will be administered electronically as secure surveys built in REDCap.

G Statistical Plan

G1 Sample Size Determination and Power

We expect vaginal cryotherapy to result in at least 3-point improvement in myofascial pain scores as reported on a 0-10 verbal pain rating scale. Prior studies investigating clinically significant reductions in pain scores report greater than 2 points on a 0-10 scale or 30% reduction in pain as clinically significant²⁸. In order to detect a 3-point difference with 80% power and alpha 0.05, we would need to enroll 30 patients per group. Accounting for a 20% loss-to-follow up rate, we plan to enroll 33 patients per group for a total of 66 patients. Patients may participate in Specific Aim #1 only, in Specific Aim #2 only, or both Specific Aims. If no patients participate in both Specific Aim #1 and Specific Aim #2, then 132 patients will be required overall.

G2 Interim Monitoring and Early Stopping

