In order to ensure the confidentiality of study participants, recruitment and consent will occur in a private examination or consult room. Patients will have ample time to ask questions of the study personnel. Patients will be determined to be eligible based on examination findings at the time of their initial evaluation. Medical record review will occur to confirm eligibility. Study-related activities will occur in a private examination room. Only the research team will have access to paper data, which will be stored in a locked cabinet in the FPMRS offices. Enrolled patients will be assigned unique study identification numbers. A password-protected electronic database will be established using REDCap, and only the research team will have access. No results will be presented in a personally identifiable manner

H2 Case Report Forms and Source Documents

All data will be securely stored in REDCap. Consent documents and hard copy documents will be securely stored in a locked cabinet in the FPMRS offices.

H3 Records Retention

Records of participating patients will be maintained throughout the study and data analysis. Records will be securely destroyed at the earliest possible time after completion of the study. Patients requesting withdrawl from the study and requesting any previously-captured results/data also be destroyed will have this information securely destroyed at the time of receipt of the request.

I Study Administration

I1 Organization and Participating Centers

The Female Pelvic Medicine & Reconstructive Surgery Division at Washington University in St. Louis is organizing and conducting this study. There are no other participating centers.

I2 Funding Source and Conflicts of Interest

This study is being funded by the Female Pelvic Medicine & Reconstructive Surgery Division at Washington University in St. Louis. All study personnel are without conflicts of interest.

I3 Subject Stipends or Payments

Study subjects will not be paid for their participation in this study.

I4 Study Timetable

Participation in this still will occur over 2 weeks. On average, we see about 30 new patients per month. Analysis from our cross-sectional data suggests that pelvic floor myofascial pain of at least 4/10 in severity is present in about 57% of new patients, thus we anticipate enrollment to take approximately 4-8 months, depending on the number of patients who choose to participate in both Specific Aims.

J Publication Plan

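### F1 fixes the trial at 66 patients, but G1 needs 66 for each aim, and E2 and G1 disagree on who may enter which aim

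*Combined protocol and SAP*

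**What the plan says.** - **F1 (Screening for Eligibility)** gives one total for the trial: "We will enroll a total of 66 patients for the trial".
- **G1 (Sample Size Determination and Power)** starts from 30 per group: "In order to detect a 3-point difference with 80% power and alpha 0.05, we would need to enroll 30 patients per group". It then allows for attrition: "Accounting for a 20% loss-to-follow up rate, we plan to enroll 33 patients per group for a total of 66 patients". The participation rule follows: "Patients may participate in Specific Aim #1 only, in Specific Aim #2 only, or both Specific Aims". G1 ends with a contingency: "If no patients participate in both Specific Aim #1 and Specific Aim #2, then 132 patients will be required overall".
- **E2, 2.a Inclusion Criteria** gives a narrower rule: "Eligible patients may participate in Specific Aim 1 only or in both Specific Aims 1 and 2".
- **I4 (Study Timetable)** takes about 30 new patients a month, of whom about 57% have pain of at least 4/10, and concludes: "thus we anticipate enrollment to take approximately 4-8 months, depending on the number of patients who choose to participate in both Specific Aims".
- **G3 (Analysis Plan)** gives each aim its own primary outcome and its own comparison between arms.

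**The concern.** F1's total carries no condition, whereas the totals in G1 and I4 depend on how many patients do both aims. They agree only at complete overlap, which neither E2 nor G1 requires. Staff who follow F1 would stop at 66, however many had declined the home-use phase.

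The two participation rules also lead to different totals. G1's 132 case needs patients who enter Aim 2 alone, a route that E2 does not offer. Under E2, if nobody did both aims, Aim 2 would have no patients at all.

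At stake is the size of Aim 2, the two-week comparison. G1 implies 33 per group at 80% power for it, and an enrolment stopped at 66 need not deliver that.

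**Working it through.** **1. The plan's own figures.** 2 arms x 33 = 66. Two aims with no shared patients: 2 x 66 = 132, which is G1's figure exactly. So 66 is G1's requirement per aim.

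**2. The timetable.** I4's inputs give 30 x 0.57 = 17.1 patients per month. Then 66 / 17.1 = 3.9 months and 132 / 17.1 = 7.7 months. I4 names no per-aim figure, but its 4-8 months fit a plan for 66 to 132 patients and not a fixed 66.

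**3. Head count if enrolment stops at 66 under E2's rule.** Everyone enters Aim 1 and a share p also enters Aim 2. The share p is an assumption; the documents do not state it. Aim 2 has 66p patients and its shortfall is 66(1 - p). No SD is needed. The last two columns show what filling Aim 2 would take if entry stayed open at the same share: 66 / p patients, over (66 / p) / 17.1 months.

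| Opt-in p | Aim 2 patients at 66 enrolled | Shortfall | Total needed | Months |
|---|---|---|---|---|
| 100% | 66 | 0 | 66 | 3.9 |
| 90% | 59.4 | 6.6 | 73.3 | 4.3 |
| 75% | 49.5 | 16.5 | 88 | 5.1 |
| 50% | 33 | 33 | 132 | 7.7 |

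The months are lower bounds, because 17.1 counts only the pain criterion, before E2's other exclusions and refusals.

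**4. Power for Aim 2.** Inputs from G1: 3-point difference, alpha 0.05, 20% loss. Assumptions: two-sided two-sample t-test, and the SD, which the plan does not state. Solving 30 per group at 80% power gives a standardised difference of 0.7356, hence SD = 3 / 0.7356 = 4.08. Analysed patients per arm = 33 x p x 0.8, that is 26.4, 23.76, 19.8 and 13.2 at p = 100%, 90%, 75% and 50%.

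| SD | 100% | 90% | 75% | 50% |
|---|---|---|---|---|
| 2 | 99.96% | 99.9% | 99.6% | 95.9% |
| 2.5 | 99.0% | 98.2% | 95.7% | 84.1% |
| 3 | 94.6% | 92.1% | 86.6% | 69.4% |
| 3.5 | 86.3% | 82.4% | 74.8% | 56.2% |
| 4.08 (back-calculated) | 74.6% | 69.9% | 61.6% | 44.3% |

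The 74.6% at full opt-in arises because 33 x 0.8 = 26.4 is below the 30 that G1 requires. That is a separate question about the loss allowance. Only the fall along each row belongs to this point.

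**5. The total under G1's rule.** If each aim closes at exactly 66, the total is 132 minus the number in both. Without that cap the formula fails. Suppose 50% do both, 40% Aim 1 only and 10% Aim 2 only. Aim 2 then gains 60% of entrants and fills at 66 / 0.60 = 110 enrolled, of whom 0.50 x 110 = 55 are in both. The formula would give 132 - 55 = 77, which is 33 too few.

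**The case against.** The strongest reply is that G1 is the governing section and already foresees partial overlap, that I4 allows time for it, and that F1 merely repeats the base-case total in a section on screening. The totals in step 3 down to 50% opt-in fall within I4's 4-8 months. This stands in part: a reader might infer that the plan overlooked overlap altogether, and it did not. But G1's contingency covers only the case of no overlap, it relies on an entry route that E2 lacks, and F1 does not refer to it.

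A reader might also infer that Aim 2 is underpowered, or will lose some 30 points of power. The documents do not support that. They state neither SD nor opt-in share, and at SD 2 or 2.5 power stays above 80% even at 50% opt-in. The 4.08 is only solved back from an unexplained 30 per group.

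E1 says "Patients will be followed up at two different time points in order to assess response to treatment", which could be taken as a third rule under which everyone does both aims. It is a design overview that labels each time point by its aim, so the contradiction lies between E2 and G1 only.

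G2 calls the study a pilot. That lowers the stakes, but G2 also names efficacy as something to be tested, and G1 states 80% power. The study-flow figure and consent form are not available here and may settle the participation rule. E2, F1 and G1 would still have to be matched to them.

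**Conclusion.** The point holds as an internal inconsistency with a definite consequence for head count. F1's 66 equals the requirement in G1 only if every patient does both aims, and E2 and G1 give incompatible entry rules. If enrolment stops at 66 under E2, Aim 2 misses its stated 33 per group by however many patients choose Aim 1 only. That conclusion needs no SD. The sizes of about 7, 17 or 33 patients rest on assumed opt-in shares.

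The cost in power runs from negligible to material and cannot be narrowed from the documents. Going from full to 50% opt-in after 20% loss, the fall is about 4 points at SD 2, 25 at SD 3 and 30 at SD 4.08. The plan should be corrected, but this is not evidence that Aim 2 will fail.

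**What to change.** 1. Reconcile E2 and G1 to one participation rule.
2. In F1 and G1, state the target as 66 per aim (33 per group), with enrolment continuing until each aim reaches it, so that the overall total depends on overlap. With open entry under E2's rule, that total is 66 divided by the share doing both. Use 132 minus the number in both only if each aim closes at exactly 66, and state that cap.
3. If the overall total is to remain 66, give the expected Aim 2 size and its power at a stated SD and opt-in share, instead of implying 33 per group at 80%.

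The change itself is wording in E2, F1 and G1. The price is either a less favourable stated figure for Aim 2 or recruitment longer than 3.9 months. At opt-in of 50% or more, the latter stays within I4's 4-8 months, before other exclusions and refusals.

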Patients participating in Specific Aim #1 will insert this tube into the vagina to a comfortable depth. A lubricant will be provided for comfort with tube insertion, if necessary. At the conclusion of the treatment, this tube will be washed thoroughly and given to the patient in a clean plastic baggie for use at home.

Patients in Specific Aim #2 will also be given two tubes according to the group to which they were randomized for use at home.

3.b Treatment Regimen

Both groups will be given the same instructions for use, which will include intravaginal placement of one tube for 10 minutes while resting in a supine position. A lubricant may be used for comfort with insertion.

Patients participating in Specific Aim #1 will perform their first intervention in the office with a repeat examination within 10 minutes of completing therapy. Patients participating in Specific Aims #2 will perform the intervention once daily at home. Patients will be asked to complete a short diary for each session, which will include the time of day, duration of application, pain score prior to and after application, and presence of any pelvic floor disorder symptoms prior to and after application.

3.c Method for Assigning Subjects to Treatment Groups

Randomization will be in 1:1 allocation to either vaginal cryotherapy or control. The examining physician and study PI will be blinded to treatment allocation. The research assistant will be aware of study allocation in order to provide instruction and answer questions but will not be involved in data collection or analysis.

3.d Preparation and Administration of Study Intervention

Cryotherapy and control tubes will be prepared by the investigators and stored on-site until randomization and treatment allocation. The tubes used for the cryotherapy and control interventions are identical, 10 ml conical tubes. Cryotherapy tubes (intervention arm) will be prepared using a mixture of isopropyl alcohol (2ml) and water (8ml) and stored in the freezer. Using this mixture results in a “slushy” consistency and prevents the contents of the tube from freezing solid, thus decreasing the risk of tissue injury. Control tubes will be empty and stored at room temperature.

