The appropriate tubes will be distributed by the research assistant with instructions provided for their appropriate use. Patients participating in Specific Aim #2 will be given tubes to take home with instructions to keep the tubes in the freezer or at room temperature according to their treatment assignment. The research assistant will not be blinded to the treatment allocation in order that she may answer any questions related to the intervention.

Patients will self-administer the intervention in the office (Specific Aim #1) or at home (Specific Aim #2) while resting in a supine position for 10 minutes. A lubricant may be used for comfort with tube insertion.

3.e Subject Compliance Monitoring

Patients will be asked to complete a short diary for each session, which will include the time of day, duration of application, pain score prior to and after application, and presence of any pelvic floor symptoms prior to and after application. This survey will be completed electronically via REDCap. The link will be sent via a secure email to the patient at the email address provided at the time of enrollment.

3.f Prior and Concomitant Therapy

There will be no requirement for prior therapy in order to participate in the study. Patients will be excluded from participation if they have previously used vaginal cryotherapy. All participating patients will be referred to pelvic floor physical therapy. There is frequently a delay in scheduling pelvic floor physical therapy of up to 2-3 weeks after initial referral thus this time was built into the study procedures in order to assess for the effect of cryotherapy independent of physical therapy. The 2 week follow up visit will occur concurrently or just prior to their first pelvic floor physical therapy visit.

3.g Blinding of Study Drug

The tubes are identical in appearance with the exception of the temperature to touch and contents. The tubes will be distributed to the patients by the research assistant, who is not blinded to treatment allocation. The patients will not be blinded to treatment allocation. The providers, who are blinded to treatment allocation, will not have contact with the tubes once distributed to the patient.

F Study Procedures

F1 Screening for Eligibility

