Vaginal cryotherapy is recommended routinely by the physicians and physical therapists in our Division and, to date, no adverse events related to the cryotherapy have been reported. Theoretical adverse events that could be related to use of cryotherapy in the vagina include skin irritation or injury from the temperature of the tube or trauma to the vagina related to placement of the tube.

Patients will be provided with contact information for study personnel who can be reached 24/7 to report an adverse event. At the follow up visit at 2 weeks, patients will be asked whether they experienced any adverse events. Follow up questions will be asked, as appropriate, for patients reporting adverse events during the study period. Adverse events will be monitored and recorded in the REDCap database. Adverse event reporting will occur throughout the duration of the study procedure.

Each reported adverse event will be reviewed by the members of the study team and graded according to the Dindo-Clavien classification for adverse events (see table). (32). Although this classification system is designed for surgical interventions, it is the most applicable classification system currently available for the intervention proposed in this

study. Any Class II or higher complications that are related or possibly related to the study intervention will result in a temporary cessation of enrollment and an investigation by the study team. A determination as to whether the study may resume will be made by the consensus of the study team. If more than 10% of enrolled patients report Class I complications that are related or possibly related to the study intervention, a similar process will occur.

TABLE 1. Classification of Surgical Complications

Grade	Definition
Grade I	Any deviation from the normal postoperative course without the need for pharmacological treatment or surgical, endoscopic, and radiological interventions Allowed therapeutic regimens are: drugs as antiemetics, antipyretics, analgesics, diuretics, electrolytes, and physiotherapy. This grade also includes wound infections opened at the bedside
Grade II	Requiring pharmacological treatment with drugs other than such allowed for grade I complications Blood transfusions and total parenteral nutrition are also included
Grade III	Requiring surgical, endoscopic or radiological intervention
Grade IIIa	Intervention not under general anesthesia
Grade IIIb	Intervention under general anesthesia

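### As E1 reads, Aim-1-only patients have no scheduled adverse-event question, yet they count in the denominator of the 10% Class I pause rule

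*Combined protocol and SAP*

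**What the plan says.** **Asking about harms.** F3, 3.a (Safety and Compliance Monitoring) contains one scheduled question: "At the follow up visit at 2 weeks, patients will be asked whether they experienced any adverse events". The other route depends on the patient: "Patients will be provided with contact information for study personnel who can be reached 24/7 to report an adverse event". The same section says in general terms that reporting runs throughout the study, without adding another occasion for asking. The home diary in E3, 3.e covers time of day, duration, and "pain score prior to and after application, and presence of any pelvic floor symptoms prior to and after application". No adverse-event item is listed.

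**Who has a two-week follow-up.** E1: "Follow-up times include immediately after application (Specific Aim #1) and two weeks following use of the intervention alone (Specific Aim #2". E2, 2.a: "Eligible patients may participate in Specific Aim 1 only or in both Specific Aims 1 and 2". G1 also allows Aim 1 alone, and adds Aim 2 alone.

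**Exposure of Aim 1 patients.** E3, 3.a says that after the office session "this tube will be washed thoroughly and given to the patient in a clean plastic baggie for use at home". E3, 3.d places self-administration in the office for Aim 1 and at home for Aim 2, and mentions take-home tubes only for Aim 2.

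**Pause rules.** One related or possibly related event of Class II or higher pauses enrolment. For milder events, a similar process follows "If more than 10% of enrolled patients report Class I complications that are related or possibly related to the study intervention". Planned enrolment is 66 (33 per arm), or 132 if nobody takes part in both aims (G1).

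**The concern.** The Class I rule compares a count of patients who report with a count of patients enrolled. That works as intended if everyone in the denominator had the same opportunity to report. If Aim-1-only patients have no two-week visit, they enter the denominator in full but reach the numerator only by calling in. Mild events are the ones a patient is least likely to call about, and Class I is the mild category.

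Two things are at stake. The sponsor's own trigger would respond at a higher true rate than its stated 10%. Any summary of harms that divides by all enrolled would also record patients who were not asked as patients without an event. This matters more if Aim-1-only patients use the tube at home, because their exposure then continues after the supervised session.

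**Working it through.** **Step 1: the trigger as a count.** The plan gives 10% with no derivation, so there is no calculation of its own to reproduce. The smallest count above 10% of N is floor(0.10 × N) + 1.
- N = 66: 7 reporters (7/66 = 10.6%).
- N = 132: 14 reporters (14/132 = 10.6%).

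**Step 2: what the trigger means among patients who are asked.** Let f be the share of enrolled patients who are not asked and do not call in. The documents do not give f, so it is assumed. The rate among those asked that is needed to trigger is 7 / (66 × (1 − f)).
- f = 0: 7/66 = 10.6%.
- f = 0.25: 7/49.5 = 14.1%.
- f = 0.50: 7/33 = 21.2%.

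This step needs no assumption about which arm the events come from.

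**Step 3: chance of triggering, single look at 66.** Assume a true Class I rate p = 0.20 in the cryotherapy arm, none in control, and reports only from patients who are asked. Let n be the number of cryotherapy patients asked. The probability is P(X ≥ 7) for X ~ Binomial(n, p).

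| Aim-1-only share | n asked (cryotherapy) | P at p = 0.20 | P for p = 0.10 to 0.30 |
|---|---|---|---|
| 0 | 33 | 0.50 | 0.04 to 0.91 |
| 25% | 24 | 0.19 | 0.007 to 0.61 |
| 50% | 16 (17) | 0.03 (0.04) | 0.001 to 0.18 (n = 16) |

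Half of 33 is 16.5, so both roundings are shown. The expected counts explain the fall: 0.20 × 33 = 6.6 reports (10.0% of 66) if all are asked, and 0.20 × 16.5 = 3.3 (5.0% of 66) if half are.

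**Step 4: the same scenario as a running rule.** F3 fixes no single look, so the rule can trigger earlier on fewer reports, for example 3 of 20. I simulated 66 patients with 33 per arm in random order, counted events at enrolment, and checked the rule after each patient.
- Checked from 20 enrolled onward: about 74% if all are asked, about 22% if half are.
- Checked from 30 enrolled onward: about 69% and 15%.

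**Step 5: sensitivity.**
- If patients who are not asked still call in half of their events, the single-look figure at f = 0.50 is about 0.22, not 0.04.
- If 132 are enrolled with no overlap between aims, 33 cryotherapy patients are asked and 14 reporters are needed. The single-look chance at p = 0.20 is then 0.003, against 0.45 if all 66 cryotherapy patients were asked.

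**The case against.** **A reader might infer that Aim-1-only patients are certainly never asked.** The documents do not settle this. The two-week question in F3 is put to patients without limit by aim. F2 sets data collection at baseline and two weeks for everyone, I4 describes two weeks of participation, and E3, 3.f links the two-week visit to physical therapy, to which all participants are referred. G3 gives Aim 1 questionnaire-change outcomes that would need later contact. If Aim-1-only patients do attend at two weeks, the gap closes. E1 points the other way, so what stands is a conflict about a safety contact.

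**A reader might infer that Aim-1-only patients continue exposure at home.** E3, 3.a supports this and 3.d does not. If they do use the tube at home, the per-session diary may also reach them.

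**The forms are not shown.** The in-office and daily REDCap forms are attachments (K4), so an adverse-event item there cannot be excluded. The repeat examination within 10 minutes of therapy is also a chance to notice harm. Neither amounts to a stated commitment to ask.

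**Pooling the arms might look like an error in the rule.** It is not. F3 lists trauma from tube placement among the possible harms, and control patients insert the same tube. Counting both arms is a legitimate choice by the sponsor.

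**The consequence is limited.** Any related Class II or higher event pauses enrolment on its own, F3 reports no known events to date, and this is a pilot (G2). These points stand, and they confine the problem to Class I events.

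**Conclusion.** The point holds in a limited form. Read with E1, the plan leaves Aim-1-only patients without a scheduled adverse-event question while keeping them in the denominator of the Class I rule. Read with F2 and I4, it may not. The two readings must be reconciled, as must E3, 3.a and 3.d on home use.

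If half of 66 patients are not asked, the 10% trigger needs about 21% among those who are. In the illustrated scenario the chance of triggering falls from about 74% to 22% under continuous checking from 20 enrolled, or from 50% to 4% at a single look at 66. These sizes rest on three assumptions that the documents do not supply: the Aim-1-only share, a 20% versus 0% event rate, and no unprompted reports. A share of one half at 66 would also leave Aim 2 with only 33 patients, short of its planned 66. The direction does not depend on the exact values, provided that some patients are not asked and report less often than those who are. The Class II and higher rule is unaffected.

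**What to change.** 1. State in E1, F2 and F3 whether Aim-1-only patients have two-week contact, and reconcile E3, 3.a with 3.d on whether they use the tube at home.
2. Ask every participant the same adverse-event question twice: at the end of the office session and in a two-week REDCap survey. Add one item to the diary for anyone using a tube at home. In the office, have the patient answer on the REDCap tablet after the repeat examination. This keeps the blinded examiner from hearing answers that reveal the arm, and keeps the allocation-aware research assistant out of data collection, as E2, 2.d requires.
3. In the final report, give adverse events by arm with the number of patients asked as the denominator. This needs no unblinded tabulation during enrolment.
4. Have the sponsor state which patients its 10% rule counts. The threshold and the pause rule itself remain the sponsor's.

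The cost is one REDCap item and one automated survey, using systems the protocol already relies on. More complete reporting may make a pause trigger somewhat earlier.
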